11.2 Clinical Laboratory Variables

Descriptive statistics (n, mean, SD, minimum, median, and maximum) for clinical laboratory values (in SI units) and changes from Baseline to Visit 6/early termination (ET), as well as shift tables from Baseline to Visit 6/ET for quantitative variables, will be presented by treatment group for the following clinical laboratory variables:

Biochemistry and Endocrinology

| | |
|-----------------------------|-----------------------|
| Total cholesterol | Calcium |
| Aspartate transaminase | Uric acid |
| Phosphorus | Blood urea nitrogen |
| Alanine transaminase | Total bilirubin |
| Sodium | Creatinine |
| Alkaline phosphatase | Glucose |
| Potassium | Albumin |
| Gamma glutamyl transferase | Total protein |
| Thyroid stimulating hormone | Lactate dehydrogenase |
| Free thyroxine | |

Hematology

| | |
|---|-------------------------|
| Hemoglobin | Neutrophils |
| Hematocrit | Lymphocytes |
| Red blood cells | Monocytes |
| Platelet count | Eosinophils |
| White blood cell count – total and differential | Basophils |
| Mean corpuscular hemoglobin | Bands |
| Mean corpuscular hemoglobin concentration | Mean corpuscular volume |

Urinalysis

| | |
|------------------|--------------------|
| Glucose | pH |
| Specific gravity | Urobilinogen |
| Blood | Color |
| Ketones | Leukocyte esterase |
| Protein | Nitrate |
| Bilirubin | |

If urinalysis detects protein and/or blood, then a microscopic examination will be conducted. The microscopic examination will consist of red blood cell, white blood cell, casts, and bacteria. These variables will be listed but not summarized.

Qualitative urinalysis variables will be summarized by the number of subjects in each category and the percentage of subjects out of the total in the Safety Analysis Set with a valid result at both baseline and the given visit.

All clinical laboratory values will be listed for the Safety Analysis Set.

Clinical laboratory test values are potentially clinically important (PCI) if they meet either the low or high PCI criteria listed in [Table 2](#). The number and percentage of subjects with post-baseline PCI values will be tabulated. The percentages will be calculated relative to the number of subjects with at least 1 available post-baseline assessment per parameter. The numerator is the total number of subjects with at least 1 post-baseline PCI value. A supportive listing of subjects with post-baseline PCI values will be provided including the subject number, site, baseline, and post-baseline values.

Table 2: Criteria for Potentially Clinically Important Laboratory Tests

| Parameter | SI Unit | Lower Limit | Higher Limit |
|------------------------------|---------|-------------|-------------------------|
| Biochemistry | | | |
| Albumin | g/dL | <3g/dL | - |
| Aspartate transaminase (AST) | - | - | ≥3 x ULN |
| Alanine transaminase (ALT) | - | - | ≥3 x ULN |
| Blood urea nitrogen | mg/dl | - | >30 mg/dl or >2.5 x ULN |
| Calcium | mg/dL | <8mg/dL | >11.5mg/dL |
| Total cholesterol | mg/dL | - | >300mg/dl |
| Creatinine | mg/dl | - | >2 mg/dl or >1.5 x ULN |
| Gamma glutamyl transferase | - | - | ≥2.5 x ULN |
| Glucose | mg/dL | <55mg/dL | >160mg/dL |
| Lactate dehydrogenase | - | - | >3 x ULN |
| Phosphorus | mg/dL | <2.5mg/dL | >7mg/dL |

Table 2: Criteria for Potentially Clinically Important Laboratory Tests

| Parameter | SI Unit | Lower Limit | Higher Limit |
|-----------------------------|---------------------|--------------------------------|----------------------------------|
| Potassium | mmol/l | <3mmol/l | >5.5mmol/l |
| Thyroid stimulating hormone | - | <LLN | >2 x ULN |
| Sodium | mEq/L | <130mEq/L | >150mEq/L |
| Uric acid | mg/dL | - | >10mg/dL |
| Total bilirubin | mg/dL | - | >2 mg/dL |
| Total protein | g/dL | <5g/dL | >9g/dL |
| Hematology | | | |
| Bands | - | - | >0.27x10 ³ /µL or >5% |
| Basophils | - | - | >10% |
| Hemoglobin | g/dL | <9g/dL | >16g/dL |
| Hematocrit | % | <30% | >50% |
| Platelet count | 10 ³ /µL | <75x10 ³ /µL | >600x10 ³ /µL |
| Red blood cells | 10 ⁶ /µL | <2.5x10 ⁶ /µL | - |
| White blood cell count | 10 ³ /µL | <3x10 ³ /µL | >16x10 ³ /µL |
| Neutrophils | - | <1x10 ³ /µL or <30% | - |
| Eosinophils | % | - | >10% |
| Lymphocytes | % | <10% | >70% |
| Monocytes | % | - | >20% |
| Urinalysis | | | |
| Glucose | - | - | Positive Value (excluding trace) |
| Protein | - | - | Positive Value (excluding trace) |
| Blood | - | - | Positive Value (excluding trace) |
| Ketones | - | - | Positive Value (excluding trace) |
| Bilirubin | - | - | Positive Value (excluding trace) |

LLN=lower limit of normal value provided by the laboratory; ULN=upper limit of normal value provided by the laboratory

11.3 Vital Signs

Descriptive statistics (n, mean, SD, minimum, median, and maximum) for vital sign variables (systolic and diastolic blood pressure, pulse rate, body weight, temperature, and respiration rate), and their changes from baseline at each assessment time point will be presented by treatment group.

Body weight is collected at every visit, while height is collected only at Screening and the last scheduled visit/ET. At each visit excluding the last scheduled visit/ET, the Screening height will

be used to derive BMI values. For the last scheduled visit/ET, corresponding height and body weight will be used to calculate the BMI values. The resulting BMI values will be rounded to 1 decimal place for reporting. Descriptive statistics for BMI will be tabulated by visit and treatment group for actual values and change from baseline.

Percentiles of body weight and BMI can be normalized by sex and age using the CDC growth charts ([Kuczmarski et al. 2002](#)). Descriptive statistics of percentiles, for both, body weight, and BMI will be generated by visit and treatment group, for actual values and change from baseline.

Furthermore, the body weight percentiles can be categorized as <5th, 5th to <95th, and ≥95th percentiles, and the BMI percentiles can be categorized as: Underweight – BMI less than the 5th percentile; Healthy Weight – BMI 5th percentile up to less than the 85th percentile; Overweight – BMI 85th percentile to less than the 95th percentile; and Obese – BMI greater than or equal to the 95th percentile. Post-baseline shifts in body weight and BMI percentile category from baseline at each visit will be presented by treatment group. The data also will be presented categorically using number of subject and percentages at each visit by treatment group.

Additionally, figures with the mean change from baseline ± SD of the vital signs values (systolic and diastolic blood pressure, and pulse), weight, and BMI will be presented by treatment group and visit.

All vital sign values will be listed for the Safety Analysis Set.

All vital sign values, include an unscheduled visit, will be considered PCI if they meet either the observed value criteria or the change from baseline criteria listed in [Table 3](#). The number and percentage of subjects with PCI post-baseline values will be tabulated by treatment group. The percentages for the observed value criteria will be calculated relative to the number of subjects with at least 1 post-baseline assessment available per parameter and visit. The percentages for the change from baseline criteria will be calculated relative to the number of subjects with available baseline and at least 1 post-baseline assessment per parameter and visit. The numerator is the total number of subjects with at least 1 PCI post-baseline vital sign value. A supportive listing of subjects with post-baseline PCI values will be provided including the subject number, site, baseline, and post-baseline PCI values.

Table 3: Criteria for Potentially Clinically Significant Vital Signs

| Vital Sign Parameter | Flag | Criteria ^a | |
|---|------|-----------------------|----------------------|
| | | Observed Value | Change from Baseline |
| Sitting systolic blood pressure (mmHg) | High | ≥120 | Increase of >10 |
| | Low | <75 | Decrease of >10 |
| Sitting diastolic blood pressure (mmHg) | High | ≥85 | Increase of >10 |
| | Low | <40 | Decrease of >10 |
| Pulse rate (beats per minute) | High | ≥130 | Increase of >15 |
| | Low | ≤55 | Decrease of >15 |
| Weight (kg) | High | - | Increase of ≥7% |
| | Low | - | Decrease of ≥7% |

Table 3: Criteria for Potentially Clinically Significant Vital Signs

| Vital Sign Parameter | Flag | Criteria ^a | |
|--------------------------|------|----------------------------------|----------------------|
| | | Observed Value | Change from Baseline |
| Temperature (deg. C) | High | >39 | - |
| | Low | <35 | - |
| BMI (kg/m ²) | High | >95th percentile for age and sex | - |
| | Low | <5th percentile for age and sex | - |

BMI=body mass index

^a A post-baseline value is considered as a PCI value if its meets either the criteria for observed value or the criteria for change from baseline.

11.4 **Electrocardiogram (ECG)**

Descriptive statistics (n, mean, SD, minimum, median, and maximum) for ECG variables (heart rate, PR interval, RR interval, QRS interval, QT interval, and QTc interval) and their changes from baseline at each assessment time point will be presented by treatment group. QTc interval will be calculated using both Bazett ($QTcB = QT/(RR)^{1/2}$) and Fridericia ($QTcF = QT/(RR)^{1/3}$) corrections; if RR is not available, it will be replaced with 60/hr in the correction formula. ECG interpretation will be summarized by visit (and Visit 6/ET) and treatment group. A shift table from baseline to each visit (and Visit 6/ET) for qualitative ECG results will also be presented.

All ECG values will be listed for the Safety Analysis Set.

Electrocardiogram variable values, include unscheduled visit, will be considered PCI if they meet either the observed value criteria or the change from baseline criteria listed in [Table 4](#). The number and percentage of subjects with post-baseline PCI values will be tabulated by treatment group. The percentages for the observed value criteria will be calculated relative to the number of subjects with at least 1 post-baseline assessment available per parameter and visit. The percentages for the change from baseline criteria will be calculated relative to the number of subjects with available baseline and at least 1 post-baseline assessment per parameter and visit. The numerator is the total number of subjects with at least 1 PCI post-baseline ECG value. A listing of all subjects with post-baseline PCI value will be provided including the subject number, site, baseline, and post-baseline PCI values.

Table 4: Criteria for Potentially Clinically Important ECG Values

| ECG Parameter | Unit | Observed Value | | Change from Baseline | |
|---------------|--------------|----------------|--|----------------------|--------------|
| | | Lower Limit | Higher Limit | Lower Limit | Higher Limit |
| ECG Result | - | - | Abnormal (core lab) and clinically significant from investigator | - | - |
| Heart Rate | Beats/minute | <55 | >130 | Decrease >15 | Increase >15 |

Table 4: Criteria for Potentially Clinically Important ECG Values

| | | | | | |
|---------------|------|---|--|---|-----------------------------------|
| PR Interval | msec | - | ≥ 200 | - | - |
| QT Interval | msec | - | ≥ 440 | - | ≥ 30 and < 60 ≥ 60 |
| QTcF Interval | msec | - | ≥ 440 and < 480 ≥ 480 and < 500 ≥ 500 | - | ≥ 30 and < 60 ≥ 60 |
| QTcB Interval | msec | - | ≥ 440 and < 480 ≥ 480 and < 500 ≥ 500 | - | ≥ 30 and < 60 ≥ 60 |
| QRS Interval | msec | - | ≥ 90 | - | - |
| Rhythm | - | - | Any rhythm other than sinus rhythm* ECG evaluation – abnormal rhythm 
 • Complete Heart Block • Tachycardia • Bradycardia • Wandering Atrial Pacemaker • Ectopic Atrial Rhythm • Atrial Fibrillation • Atrial Flutter • Multifocal Atrial Tachycardia • Supraventricular Tachycardia • Atrial Bigeminy • Ventricular Bigeminy • Atrial Couplets • Ventricular Couplets • Ventricular Tachycardia • Torsade des Pointes • Ventricular Fibrillation • Junctional Rhythm • Idioventricular Rhythm • Escape Beat • Atrial Pacemaker | - | - |

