**Secondary:**

- **Key Secondary:** To evaluate the efficacy of SPD489 compared to placebo, using a global clinical measure of improvement, the Clinical Global Impression- Global Improvement (CGI-I) Scale.
- **Secondary:**
  - To evaluate the dose-response relationship in preschool children with ADHD, using the ADHD-RS Preschool Version Total Score.
  - To evaluate the safety and tolerability of SPD489 based on the occurrence of treatment-emergent adverse events (TEAEs), specific evaluation of vital signs (systolic and diastolic blood pressure and pulse), height, weight, and body mass index, clinical laboratory evaluations, electrocardiogram (ECG) results, sleep assessment, and the Columbia Suicide Rating Scale (C-SSRS).

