#### **Safety Endpoints**

Safety assessments include the occurrence of TEAEs, specific evaluation of blood pressure, pulse, height, weight, and body mass index, clinical laboratory evaluations and ECG results, sleep assessments (including sleep diary data and CSHQ), and C-SSRS.

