#### 7.2.4.5 Height and Weight

Height will be captured at the screening visit (Visit -1) and Visit 6/ET. A calibrated stadiometer must be used for all height measurements. Height should be measured in inches or centimeters without shoes with the subject standing on a flat surface and with chin parallel to the floor. The body should be straight but not rigid.

Weight will be captured at each visit to the site. The same calibrated scale must be used for all weight measurements. Weight should be measured in pounds or kilograms without shoes.

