3.2 Secondary Objectives

- **Key Secondary:** To evaluate the efficacy of SPD489 compared to placebo, using the global clinical measure of improvement, the Clinical Global Impression – Global Improvement (CGI-I) scale.
- **Secondary:**
 - To evaluate dose-response relationship in preschool children with ADHD, using the ADHD-RS Preschool Version Total Score.
 - To evaluate the safety and tolerability of SHP489 based on the occurrence of TEAEs, specific evaluation of vital signs (systolic and diastolic blood pressure and pulse), height, weight, and body mass index (BMI), clinical laboratory evaluations and electrocardiogram (ECG) results, sleep assessment, and the Columbia Suicide Rating Scale (C-SSRS).

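### Height is a stated safety endpoint with no planned post-baseline summary, and the SAP's BMI rule changes its height at Visit 6/ET, which puts an artificial downward step between Visit 5 and Visit 6

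*SAP*

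**What the plan says.** The protocol synopsis lists among its safety endpoints "specific evaluation of blood pressure, pulse, height, weight, and body mass index". The safety objective in Protocol 2.2.2 and in SAP 3.2 also names height beside weight and BMI. Protocol 7.2.4.5 fixes the measurements: "Height will be captured at the screening visit (Visit -1) and Visit 6/ET". Weight is taken at every site visit.

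SAP 11.3 sets out the vital-sign summaries for "vital sign variables (systolic and diastolic blood pressure, pulse rate, body weight, temperature, and respiration rate"), and then adds BMI, weight and BMI percentiles, category shifts and figures. Height is not among them, and SAP Table 3 has no height criterion. Protocol 9.9 does not mention height. SAP 7.1 summarises height as a demographic characteristic.

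For BMI, SAP 11.3 says: "At each visit excluding the last scheduled visit/ET, the Screening height will" be the denominator; then "For the last scheduled visit/ET, corresponding height and body weight will be used to calculate the BMI values". The resulting BMI is tabulated and plotted by visit as change from baseline, converted to CDC percentiles, shifted by category, and flagged in Table 3 below the 5th or above the 95th percentile.

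Baseline BMI is not defined in one way. The SAP 7.1 formula reads as using Screening height and weight. SAP 11 takes the last value before first dose, which means Visit 0 weight over Screening height.

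**The concern.** There are two linked problems.

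First, an endpoint that the trial measures twice in every child who attends Visit 6/ET gets no planned result after baseline. Weight and BMI get summaries, changes, percentiles, shifts and flags; height gets none of these. SAP 17 declares no departure from the protocol, so the omission is not explained.

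Second, BMI by visit is built from two different height rules. Through Visit 5 the denominator is an old, shorter height; at Visit 6/ET it is the current one. All growth since Screening is therefore booked at a single visit. The protocol itself notes that amphetamine may suppress appetite and lists decreased appetite and weight decrease among the common events. A reader of the planned BMI figure could take a drop at the last visit for a late drug effect when it comes from the derivation. Conversely, an inflated BMI at Visits 1-5 can hide a small decline, and can move a child across the percentile limits used for the shift tables and flags.

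**Working it through.** The plan states no figure to reproduce here, so the check applies the SAP's own formula, BMI = weight (kg) / height (m)², under its two-height rule and compares it with current height at every visit.

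**Inputs from the documents**
- Screening falls on Day -28 to Day -1 (Protocol Table 1), so Screening height is normally s = 1 to 28 days old at Visit 0. It can be older, because Table 1 provides for repeat safety tests after more than 30 days.
- Visit 5 is Day 35 and Visit 6 is Day 42. Screening to Visit 6 is therefore 1 + 42 = 43 to 28 + 42 = 70 days.
- BMI is reported to one decimal place.

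**Assumptions (not in the documents)**
- Screening height 108 cm and weight 18.5 kg, so Screening BMI = 18.5/1.08² = 15.86.
- Growth g = 5 to 8 cm/year; weight gain w = 0 to 2.5 kg/year; both linear.

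**Formulas**, with d = days from Visit 0
- Height(d) = 108 + g(d + s)/365 cm. Weight(d) = 18.5 + w(d + s)/365 kg.
- SAP BMI through Visit 5 = Weight(d)/1.08². SAP BMI at Visit 6 = Weight(42)/Height(42)², with height in metres.

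**Growth between the two height measurements.** Lowest: 5 × 43/365 = 0.59 cm. Highest: 8 × 70/365 = 1.53 cm. The effect on BMI is (108/108.59)² - 1 = -1.1% to (108/109.53)² - 1 = -2.8%.

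**One case in full** (g = 6, w = 2, s = 28)
- Visit 0: weight 18.5 + 2 × 28/365 = 18.653; BMI 18.653/1.1664 = 15.99.
- Visit 5: weight 18.5 + 2 × 63/365 = 18.845; BMI 18.845/1.1664 = 16.16; change +0.16.
- Visit 6: weight 18.5 + 2 × 70/365 = 18.884; height 108 + 6 × 70/365 = 109.15 cm; BMI 18.884/1.0915² = 15.85; change -0.14.
- Step from Visit 5 to Visit 6: -0.31. With current heights throughout, both changes are -0.01 and there is no step.

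**Range** (kg/m²; differences are taken before rounding)

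| g, w, s | SAP change, Visit 5 | SAP change, Visit 6 | Step, Visit 5 to 6 | Visit 6 change with current heights | Error in Visit 6 change |
|---|---|---|---|---|---|
| 5, 2.5, 1 | +0.21 | +0.07 | -0.13 | +0.08 | 0.00 |
| 6, 2.0, 1 | +0.16 | -0.01 | -0.18 | -0.01 | 0.00 |
| 6, 2.0, 28 | +0.16 | -0.14 | -0.31 | -0.01 | -0.14 |
| 5, 0, 28 | 0.00 | -0.28 | -0.28 | -0.17 | -0.11 |
| 8, 0, 28 | 0.00 | -0.44 | -0.44 | -0.26 | -0.18 |

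The step is -0.13 to -0.44 under the SAP rule and -0.04 to +0.01 with current heights. Starting from 18 kg with unchanged weight and a 28-day gap gives -0.27 to -0.43, so the starting weight matters little.

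**Where the step comes from.** In the worked case the Visit 5 change is too high by 0.16 - (-0.01) = 0.17 and the Visit 6 change too low by 0.14; together these make 0.31. The first part is growth after Visit 0 that the old height ignores. The second is growth between Screening and Visit 0, which inflates the baseline, and it vanishes when the two visits are close together.

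**The case against.** The case for leaving the plan alone has real content.

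- *The rule is explicit and follows from the schedule.* Height is measured only twice, and each visit uses the latest available value. True, but that does not make the by-visit series comparable across its last interval.
- *Visit 6 BMI is correct.* This stands. It pairs height and weight from the same visit; the errors lie at Visits 1-5 and, to a smaller degree, at baseline. A reader might infer that normal growth will show as a BMI fall from baseline at Visit 6. The documents and the arithmetic do not support that as a general statement: with ordinary weight gain and a short screening gap the Visit 6 change is close to zero. The drop is mainly relative to Visit 5.
- *All arms share the rule.* This also stands. A reader might infer a biased drug-placebo contrast; at the same visit there is none if growth and visit timing are equal. The protection is weaker for early-termination children, whose height switches earlier, if stopping differs by arm.
- *Weight already covers appetite effects.* Weight, its percentiles and shifts, and the 7% change flag do not use height and are unaffected. BMI output is descriptive only. This limits the consequence but does not supply a height result.
- *Height may be in the table shells.* SAP 1 puts these in a separate document, which cannot be checked here. Protocol 9.4 nevertheless assigns methods and definitions to the SAP.

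Two further readings go too far. Height is not left out of all analysis, since SAP 7.1 summarises it at baseline and Visit 6 height enters BMI. Nor is Screening height always at least four weeks old at dosing; within the planned schedule, 28 days before Visit 0 is the upper end.

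**Conclusion.** The point holds in this form. SAP 11.3 specifies no summary of post-baseline height or height change, although height is a stated safety objective and endpoint and the data are collected. That part rests on the text alone.

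The change of denominator at Visit 6/ET adds an artificial step of about -0.13 to -0.44 kg/m² between Visit 5 and Visit 6 under the assumed growth, weight gain and screening gap. At one-decimal reporting it would be visible. The error in the Visit 6 change from baseline is smaller, 0.00 to -0.18 kg/m². The affected outputs are the within-arm BMI trend figure, the BMI percentile and category shifts, the BMI percentile flags, and early-termination children. The primary and key secondary efficacy analyses are untouched. The change should be made, but it is a correction to safety reporting and not a threat to the trial's conclusions.

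**What to change.** In the SAP:

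1. In 11.3, add descriptive statistics for height and height-for-age percentile (the CDC charts are already cited) at Screening and Visit 6/ET, with change, by dose arm, pooled doses and placebo. Note that the interval includes the screening period.
2. Make the BMI change, percentile-shift and category analysis the one from Screening to Visit 6/ET, using height and weight measured at the same visit. Use weight and weight percentile for by-visit trends. Footnote any BMI shown for the visits in between as based on Screening height.
3. State which BMI is baseline, so that 7.1 and 11 agree.

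Interpolating height between the two measurements is a possible alternative, but it makes baseline BMI depend on a post-randomisation height, and children who drop out without that measurement or are still ongoing at the interim analysis would lack it.

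The cost is SAP wording and one extra table, with no new data. The BMI change interval will include up to about four weeks before dosing, and children with no Visit 6/ET height cannot contribute to the change, so the number analysed should be shown by arm.

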11.1 Adverse Events

Adverse events will be coded using Version 18.0 or newer of the Medical Dictionary for Regulatory Activities.

An AE (classified by preferred term [PT]) that occurs during the Evaluation Period will be considered a TEAE if it has a start date on or after the first dose of investigational product or if it has a start date before the date of the first dose of investigational product, but increases in severity on or after the date of the first dose of investigational product. If more than 1 AE with the same PT is reported before the date of the first dose of investigational product, then the AE with the greatest severity will be used as the benchmark for comparison to the AEs occurring during the Evaluation Period under the preferred term. An AE that occurs more than 3 days after the date of the last dose of investigational product will not be counted as a TEAE.

An overall summary of number of subjects with TEAEs in each treatment group will be presented by treatment group, including the number and percentage of subjects with any TEAEs, serious TEAEs, TEAEs related to investigational product, TEAEs leading to withdrawal, severe TEAEs, and TEAEs leading to death.

Number and percentage of subjects reporting TEAEs in each treatment group will be tabulated by system organ class (SOC) and PT. TEAEs will be further summarized by maximum severity and relationship to investigational product. If more than 1 AE occurs with the same PT for the same subject, then the subject will be counted only once for that PT using the most severe and most related occurrence for the summarization by severity and by relationship to investigational product.

The incidence of TEAEs, serious TEAEs, and TEAEs leading to withdrawal will be summarized by SOC, PT, and treatment group, sorted in decreasing frequency for subjects on SPD489 then for placebo. The incidence of common ($\geq 2\%$ of subjects in any treatment group) will be summarized by PT and treatment group, sorted in decreasing frequency for subjects on SPD489 and then for placebo.

The number and percentage of subjects reporting TEAEs over the Safety Analysis Set will also be presented by week of AE onset, preferred term and treatment group, where week of AE onset is calculated as (AE occurred date – first dose date + 1) / 7, then rounded up to an integer.

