18.3 Repeated or Unscheduled Assessments of Safety Parameters

If a subject has repeated assessments before the start of investigational product, then the results from the final assessment made prior to the start of investigational product will be used as baseline. If end-of-study assessments are repeated or unscheduled, the last post-baseline assessment while on investigational product will be used for generating descriptive statistics. However, all post-baseline assessments will be used for PCI value determination and all assessments will be presented in the data listings.

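### In SAP 11.2 to 11.4 the observed-value counts of potentially clinically important (PCI) findings ignore baseline status, so findings present before the first dose are mixed with new ones

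*SAP*

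**What the plan says.** The numerator is the same in all three domains and carries no condition on the baseline value.

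- SAP 11.2, laboratory: "The numerator is the total number of subjects with at least 1 post-baseline PCI value".
- SAP 11.3, vital signs: "The numerator is the total number of subjects with at least 1 PCI post-baseline vital sign value".
- SAP 11.4, ECG: "The numerator is the total number of subjects with at least 1 PCI post-baseline ECG value".

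In 11.3 and 11.4, percentages for the observed-value criteria "will be calculated relative to the number of subjects with at least 1 post-baseline assessment available per parameter and visit", so the denominator does not even require a baseline value. The laboratory denominator is built the same way. A footnote to Table 3 makes the two kinds of criterion alternatives: "A post-baseline value is considered as a PCI value if its meets either the criteria for observed value or the criteria for change from baseline". SAP 18.3 adds that "all post-baseline assessments will be used for PCI value determination".

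Adverse events are handled differently. Under SAP 11.1, an event that began before dosing is treatment-emergent only "if it has a start date before the date of the first dose of investigational product, but increases in severity" on or after the first dose.

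Baseline does appear near the PCI tables. For vital signs, "A supportive listing of subjects with post-baseline PCI values will be provided including the subject number, site, baseline, and post-baseline PCI values", and the laboratory and ECG listings are similar. SAP 11.2 plans laboratory shift tables for quantitative variables, 11.3 plans shifts in weight and BMI percentile category, and 11.4 plans a shift table for qualitative ECG results.

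**The concern.** A PCI table is normally read as a screen for what happened on treatment. Under this rule an entry can mean a new abnormality or one the child brought into the study, and the table cannot tell the reader which. The carried-over part adds a background to every arm. That background raises all the rates, pulls a ratio between arms toward 1, and varies by chance from arm to arm. SAP 11 reports safety by individual dose strength, so chance variation in the background could be taken for a dose pattern.

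**Working it through.** **1. Which criteria are exposed.** A change-from-baseline criterion cannot be met before dosing, so only observed-value limits can carry over.

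| Criterion | Change criterion too? | Other protection in the documents | Exposure |
|---|---|---|---|
| Laboratory limits (Table 2) | No | Shift tables, not stated to use the PCI limits | Full |
| Urinalysis positives (Table 2) | No | None: the shift tables are for quantitative variables | Full |
| PR, QRS, rhythm (Table 4) | No | Shift table covers the qualitative ECG result only | Full |
| Low blood pressure, pulse (Table 3); heart rate, QT/QTc (Table 4) | Yes | The change criterion shows on-treatment movement | Partial |
| BMI percentile (Table 3) | No | Category shifts at each visit (11.3); baseline BMI category by group (7.1) | Largely answered |
| High blood pressure (Table 3) | Yes | Eligibility | None in practice |
| Weight (Table 3) | Change criterion only | Not needed | None |

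For high blood pressure, protocol exclusion 9 removes children at or above the 95th percentile at screening or baseline. In protocol Appendices 2.3 and 2.5 the highest tabled values at ages 4 and 5 are 116 systolic and 74 diastolic. The PCI limits are 120 and 85.

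**2. Arm sizes.** The plan's total reproduces: 156/(1 − 0.20) = 195. At 5:5:5:5:6, each drug arm has 195 × 5/26 = 37.5 children, placebo has 195 × 6/26 = 45, and pooled 10 to 30 mg has 195 × 15/26 = 112.5.

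**3. Size of the carry-over (assumed).** Let q be the share of children who meet a criterion at baseline and still meet it later. The documents give no value, so q = 5%, 10% and 15% are shown. Expected carried-over counts are q × n.

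| q | One drug arm (37.5) | Placebo (45) | Pooled 10–30 mg (112.5) | All (195) |
|---|---|---|---|---|
| 5% | 1.9 | 2.2 | 5.6 | 9.8 |
| 10% | 3.8 | 4.5 | 11.2 | 19.5 |
| 15% | 5.6 | 6.8 | 16.9 | 29.2 |

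**4. Effect on the contrast.** If i is the new-onset rate among children not PCI at baseline, the SAP rule displays q + (1 − q) × i. Take i = 2% on placebo and 6% on active, both assumed. For example, at q = 10% placebo is 0.10 + 0.90 × 0.02 = 11.8% and active is 0.10 + 0.90 × 0.06 = 15.4%.

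| q | Placebo | Active | Risk ratio | Risk difference (points) |
|---|---|---|---|---|
| 0 | 2.0% | 6.0% | 3.0 | 4.0 |
| 5% | 6.9% | 10.7% | 1.55 | 3.8 |
| 10% | 11.8% | 15.4% | 1.31 | 3.6 |
| 15% | 16.7% | 20.1% | 1.20 | 3.4 |

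The ratio falls sharply. The difference shrinks only by the factor 1 − q.

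**5. Noise.** Suppose there is no drug effect and carry-over is binomial, with 38 children in each of four drug arms and 45 on placebo. The standard deviation of one arm-to-placebo difference is √[q(1 − q)(1/38 + 1/45)]. At q = 10% this is √[0.09 × 0.0485] = 6.6 points. The chance that at least one of the four arms differs from placebo by 10 points or more, in either direction, is Σₐ P(A = a) × {1 − [1 − P(|K/38 − a/45| ≥ 0.10)]⁴}, where A and K are the binomial counts on placebo and in a drug arm. This gives about 13%, 36% and 50% at q = 5%, 10% and 15%.

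**The case against.** The SAP calls these values post-baseline and never treatment-emergent, and a prevalence-type screening table is a recognizable descriptive choice. No hypothesis test or stopping rule depends on it. Protocol exclusion 11 removes clinically significant laboratory and ECG abnormalities at entry, and the Table 4 ECG-result criterion needs an investigator's rating of clinical significance. Most parameters of direct concern for a stimulant (blood pressure, pulse, weight, heart rate, QT/QTc) have change criteria, and protocol 8.1.5 lets normal-to-abnormal shifts be recorded as adverse events. The listings let a reader separate old from new by hand.

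Much of this stands, and it rules out four stronger readings.

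- A reader might infer that the plan presents pre-existing findings as treatment-emergent. The wording does not do that; the tables simply fail to separate the two.
- A reader might infer bias for or against the drug. Randomization gives every arm the same expected carry-over.
- A reader might take BMI as the leading case, since no criterion limits high BMI. A child above the 95th percentile before and after dosing would indeed be flagged, but would also appear as unchanged in the planned category shift table.
- A reader might include high blood pressure, which eligibility effectively removes.

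What the objection does not meet is the case of the laboratory, urinalysis, PR, QRS and rhythm limits. Exclusion 11 rests on investigator judgment rather than on the PCI limits, and the planned shift tables are either not stated to use those limits or do not cover these criteria. The listings leave the table counts unchanged.

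**Conclusion.** The point holds as a reporting weakness of limited scope. For observed-value criteria the PCI tables cannot separate new findings from old. This is fully so for Table 2 and for PR, QRS and rhythm, and only partly so for low blood pressure, pulse, heart rate and QT/QTc. The consequence is higher displayed rates, a weaker relative contrast and extra chance variation between small arms. Absolute differences are little affected. Every figure for size rests on assumed carry-over, full persistence of the baseline finding and assumed new-onset rates, so the figures show direction and plausible range, not what this trial would find. If few children meet these limits at entry, the effect is small. The primary and key secondary efficacy analyses are untouched.

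**What to change.** In SAP 11.2, 11.3 and 11.4, for each observed-value criterion:

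1. Report the number and percentage of children with a post-baseline PCI value among those who have a baseline value that did not meet that criterion.
2. Add a cross-tabulation of baseline by post-baseline PCI status by treatment group, using the same limits and, for QTcF and QTcB, the bands already in Table 4. The restriction in step 1 alone would drop a child who was abnormal at baseline and became worse. The cross-tabulation keeps children abnormal at baseline visible, including those who move to a worse category.
3. For the ECG intervals, state whether baseline status is judged on the mean of the three Visit 0 tracings (protocol 7.2.4.7) or on the last value before dosing (SAP 11).

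Keep the change-from-baseline criteria, the use of all post-baseline assessments in 18.3, and the listings.

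No new data are needed, because baseline or screening values are already collected. The cost is SAP wording, one programming condition, one more table per domain and somewhat smaller denominators. At an assumed 10% carry-over, a drug arm would go from 37.5 to 37.5 × 0.90 = 33.75 children for that criterion.
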